ANNEX 2. ENCEPP CHECKLIST FOR STUDY PROTOCOLS

Not applicable

**1 Methods for calculation of derived variables**

Age at registration: Year of registration {year(registration.registered\_at)} - Year of birth {patient.birthyear}

Clinical COPD Questionnaire (CCQ): Each of the 10 CCQ questions is scored by the patient on a 7-point scale between 0 (Never/Not limited at all) and 6 (Almost all the time/Totally limited or unable to do) at baseline and end of the observation after approximately 6 weeks. The (total) CCQ score measures the health and functional status. A higher CCQ score is indicative of worse status and a decrease of 0.4 points is considered to be the minimum clinically important difference (MCID). The total CCQ score and the corresponding subscales are calculated as followed, in case that at least the number of required answers is available:

Scale	Items	Items required	Scoring (For details see www.ccq.nl)	Field names
Symptom	1; 2; 5; 6	3	$\frac{\text{Sum of answered questions}}{\text{Number of answered questions}}$	ccq.q_ [01;02;05;06]
Functional state (CCQ-4)	7-10	3	$\frac{\text{Sum of answered questions}}{\text{Number of answered questions}}$	ccq.q_07- ccq.q_10
Mental state	3; 4	2	$\frac{\text{Item 3} + 4}{2}$	ccq.q_03; ccq.q_04
Total CCQ score	All subscales must be calculable		$\frac{(\text{Symptom} + \text{Functional state}) * 4 + (\text{Mental state}) * 2}{10}$	ccq.q_01- ccq.q_10

Change of CCQ score: total CCQ score at baseline minus total CCQ score after approximately 6 weeks

Therapeutic success: total CCQ score at baseline minus total CCQ score after approximately 6 weeks is greater or equal to 0.4

Non therapeutic success: total CCQ score at baseline minus total CCQ score after approximately 6 weeks is less than 0.4

Share of patients with therapeutic success: number of patients with therapeutic success divided by total number of patients

mMRC questionnaire {mmrc.activity}:

mMRC Classification	Answer
Grade 0	Breathless with strenuous exercise
Grade 1	Short of breath when hurrying on the level or walking up a slight hill
Grade 2	Walk slower than people of the same age on the level because of breathlessness, or have to stop for breath when walking at own pace on the level
Grade 3	Stop for breath after walking about 100 meters or after a few minutes on level
Grade 4	Too breathless to leave the house or breathless when dressing or undressing

GOLD group

GOLD group	Definition	Exacerbations* per year {anamnesis.exacerbation} and/or hospitalizations due to exacerbations {anamnesis_exacerbation_hospital}	mMRC classification {mmrc.activity}
A		0-1 and =0	≤1
B	Low risk, more symptoms	0-1 and =0	≥ 2
C	High risk , less symptoms	≥ 2 or ≥1	0-1
D	High risk , more symptoms	≥ 2 or ≥1	≥ 2

\*For unknown number of exacerbations "0" is included in the calculation of the GOLD group

If 0 or 1 exacerbation per year is documented along with a mMRC of at least grade 2 at baseline the patient is assigned GOLD group B.

If two and more exacerbations per year are documented along with a mMRC of grade 0 or 1 at baseline the patient is assigned GOLD group C.

If two and more exacerbations per year are documented along with a mMRC of at least grade 2 at baseline the patient is assigned GOLD group D.

Duration between initial diagnosis of COPD and baseline visit: Year of Visit 1 {year(anamnesis.date)}- Year of initial COPD diagnosis {anamnesis.copd\_year}

Time between start of treatment and end of observation/discontinuation [weeks]: (Date of Visit 2 {visit.date}/Date of last treatment within observation period {visit.spioalto\_last\_date}- Date of start of treatment {anamnesis.spioalto\_date})/7

Time between Visit 1 and Visit 2 [weeks]: (Date of Visit 2 {visit.date}-Date of Visit 1 {anamnesis.date})/7

Pack years: (Years of smoking)\*(Cigarette parcels per day){anamnesis.smoker\_pack\_years; visit.smoker\_pack\_years}

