Data analysis:	
Primary outcome: “Therapeutic success” at visit 2 (0.4 - point decrease in the CCQ score from visit 1 to visit 2).
 
Secondary outcomes: Change in the CCQ and CCQ-4 score from visit 1 to visit 2. General condition of the patient, evaluated by the physician (PGE-score) at visit 1 and visit 2 Patient satisfaction with Spiolto® Respimat® at visit 2 Patient’s willingness to continue treatment Subgroup analysis for maintenance naïve patients and the ones already treated at baseline with long acting bronchodilators or LABA + ICS will be performed for the primary outcome. Subgroup analyses will be performed by GOLD spirometric classifications (2 vs. 3 vs. 4) and GOLD patient groups (B vs. C/D and B vs. C vs. D) for the primary outcome and changes in CCQ score for the secondary outcome
		
Milestones:	Start of data collection	Q2 2017	
	End of data collection	Q2 2018	
	Final report of study results	Q3 2018	

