9.2.3 Study visits

Patients will be enrolled consecutively and will be followed over an observational period of approximately 6 weeks. Data as listed in [Table 9.2.3.1](#) will be collected.

Proprietary confidential information © 2017 Boehringer Ingelheim International GmbH or one or more of its affiliated companies

Two study visits will be performed. At Visit 1 (baseline) the patient will be included into the NIS. At visit 2, after approximately 6 weeks from baseline, the observation of the patient will end. The respective exams and data to be collected are listed in Table 9.2.3.1.

Table 9.2.3.1: Visit flow chart and data collection parameters

Parameter	Visit 1; baseline visit	Visit 2; approx. 6 weeks after baseline visit
Informed Consent	X	
Inclusion / Exclusion Criteria	X	
Patient demographics (age, gender, height, and weight)	X	
Start of COPD	X	
Number of exacerbations in the last 12 months	X	
Number of exacerbations leading to hospitalization in the last 12 months	X	
mMRC breathlessness scale, completed by the patient	X	
Past COPD therapies (6 weeks before visit 1)	X	
Respimat [®] training (yes/no)	X	
COPD severity based on GOLD assessment ¹	X	
GOLD spirometric classification, if available ²	X	
Smoking history	X	X
Concomitant diseases / Comorbidities	X	X
COPD related and other relevant concomitant medication	X	X
Health and functional status by CCQ questionnaire, completed by patient	X	X
General condition of patient evaluated by Physician's Global Evaluation (PGE)	X	X
Safety: Adverse Drug Reactions (serious and non-serious), fatal AE, pregnancy	X	X
Patient satisfaction with Spiolto [®] Respimat [®]		X
Rationale for Spiolto [®] Respimat [®] treatment discontinuation (if applicable)		X
Continuation or discontinuation of treatment with Spiolto [®] Respimat [®] after the study (yes/no)		X

¹ GOLD patient group (B, C or D) will be automatically calculated within the eCRF based on available exacerbation history and mMRC.

² GOLD stage 1-4 spirometric classification of airflow limitation based on post-bronchodilator FEV₁ if available.

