9.7.3 Handling of missing data

For rules regarding the imputation of CCQ score, refer to www.ccq.nl (Section health care professionals, Scoring, missing data rules). No other missing data will be imputed. Every effort will be made to collect complete data at the specified time points. Any removal from the analysis will be documented, stating the site and patient number as well as the reason for removal.

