**Table 15.1.4 12: Treated Set- COPD degree of severity (GOLD group)**

COPD degree of severity (GOLD group)	N	%
A		
B		
C		
D		
Missing		
Number of patients in Treated Set		

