**Table 15.1.4 14: Treated Set- COPD degree of severity (GOLD group) – Distribution**

GOLD stadium- Distribution		A		B		C		D		Missing	
Symptoms	Exacerbations	N	%	N	%	N	%	N	%	N	%
0-1	0-1										
	>=2										
2-4	0-1										
	>=2										
Number of patients in Treated Set											

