**2.4 Sensitivity analysis II- Non-estimated number of exacerbations\***

\*If the physician does not know the exact number of exacerbations he is allowed to give an estimate. In this analysis only those documentations are considered in which the physician knew the exact number, i.e. the number is not estimated (non-estimated).

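### The SAP counts an unknown exacerbation history as zero when deriving the GOLD group, against the protocol's missing-data rule, and its written GOLD rule disagrees with its own table on hospitalised exacerbations

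*SAP*

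**What the plan says.** **Unknown counts.** The GOLD table in SAP Section 1 carries the footnote "For unknown number of exacerbations '0' is included in the calculation of the GOLD group". Protocol 9.7.3 refers to the CCQ scoring rules and adds "No other missing data will be imputed". Protocol 9.6 lists unknown answers together with missing data in its description of the eCRF checks. The footnote to Table 9.2.3.1 in Protocol 9.2.3 says "GOLD patient group (B, C or D) will be automatically calculated within the eCRF based on available exacerbation history and mMRC".

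**Hospitalisation.** In the SAP table, groups C and D need at least 2 exacerbations or at least 1 hospitalisation for an exacerbation; groups A and B need 0 to 1 exacerbations and no hospitalisation. Three sentences below the table restate B, C and D from the exacerbation count and mMRC alone. The one for B begins "If 0 or 1 exacerbation per year is documented along with a mMRC of at least grade 2 at baseline". No sentence defines A.

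**Use.** The protocol abstract plans subgroup analyses by "GOLD patient groups (B vs. C/D and B vs. C vs. D) for the primary outcome" and for change in CCQ score. SAP 2.5 repeats these groupings and attaches p-values (Subgroup Tables 2 and 5). The same variable feeds Tables 15.1.4 12 to 16.

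**Sensitivity analysis II** (SAP 2.4) repeats the GOLD tables on a restricted set: "In this analysis only those documentations are considered in which the physician knew the exact number".

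**The concern.** Setting an unknown count to zero is single-value imputation of a classification variable, and zero is the lowest possible value. Any error therefore moves patients from high to low risk. A true D patient counted as B dilutes group B. A true C patient counted as A leaves the B vs C/D comparison and appears to be in a group that the inclusion criteria exclude, although the eCRF calculation described in the protocol returns only B, C or D.

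The SAP is also inconsistent with itself. Its sentence for B requires a documented count. Table 15.1.4 10 has a missing-value column for exacerbations, so the same patient can be missing there and zero for GOLD.

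The conflict over hospitalisation is separate: two rules for one variable stand in the same section, and they give different answers for a patient whose single exacerbation led to admission.

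**Working it through.** The plan gives no figure for unknown counts or for single hospitalised exacerbations. Its study-size figures are not in dispute and reproduce: 0.5 ± 1.96·√(0.25/1170) gives 47.1% to 52.9%, and 1170/0.9 = 1300.

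**Step 1. Enumerate the patterns.** Take the count as 0, 1, ≥2 or unknown, hospitalisation as 0 or ≥1, and mMRC as 0–1 or ≥2. Dropping the impossible count 0 with hospitalisation ≥1 leaves 7 × 2 = 14 patterns.

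**Step 2. Unknown counts (4 patterns).** With hospitalisation ≥1 the table gives C or D whatever the count. The footnote alone decides the other two.

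| Count | Hospitalisation | mMRC | Group under footnote | Group if the true count is ≥2 |
|---|---|---|---|---|
| unknown | 0 | ≥2 | B | D |
| unknown | 0 | 0–1 | A | C |

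No pattern moves upward.

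**Step 3. Recorded counts (10 patterns), table against sentences.** Six agree. The other four are:

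| Count | Hospitalisation | mMRC | Table | Sentences |
|---|---|---|---|---|
| 1 | ≥1 | ≥2 | D | B |
| 1 | ≥1 | 0–1 | C | none |
| 0 | 0 | 0–1 | A | none |
| 1 | 0 | 0–1 | A | none |

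**Step 4. Effect of the footnote on B vs C/D.** If a share f of the observed group B is truly D and has the C/D success rate, the observed B rate is (1−f)·p_B + f·p_CD. The observed difference is then (1−f)(p_B − p_CD).

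Among patients with mMRC ≥2, let u be the share with an unknown count, h the share truly high risk (taken as equal for known and unknown counts), and k the share of high-risk patients with unknown counts who are kept in D by a recorded hospitalisation. Then

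f = u·h·(1−k) / [(1−u)(1−h) + u(1−h·k)].

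All three inputs are assumptions: u 1% to 10%, h 30% to 50%, k 25% to 50%.

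| u | h | k | f | True 10 points reads |
|---|---|---|---|---|
| 0.01 | 0.3 | 0.5 | 0.0015/0.7015 = 0.21% | 9.98 |
| 0.05 | 0.5 | 0.25 | 0.01875/0.51875 = 3.61% | 9.64 |
| 0.10 | 0.5 | 0.25 | 0.0375/0.5375 = 6.98% | 9.30 |

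A second set of assumptions takes 1170 patients all with mMRC ≥2, h 20% to 40%, u 5% to 20%, k = 0, and success of 55% in B and 45% in D. It moves 12 to 94 patients and gives f of 1.2% to 11.8%, so that 10 points reads 9.9 to 8.8.

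**Step 5. What Sensitivity analysis II covers.** By its wording it drops unknown counts, and its Table 12 gives success by GOLD group. It has no B vs C/D contrast and no CCQ-change table. Its Table 6 has only No and Yes rows, so how unknown counts are coded is not stated. It does not touch the hospitalisation conflict.

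**The case against.** **The effect is small.** With 1170 patients split equally and success near 50%, the 95% half-width for B vs C/D is 1.96·√(2·0.25/585) ≈ 5.7 points. A shift of 0.7 points is about one-eighth of that, and Protocol 9.7 disclaims formal testing. This stands: the case rests on the conflict with the protocol and the one-way direction, not on size.

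**The table evidently governs.** It alone carries the eCRF field names, and a C or D entry in a 0–1 exacerbation row of Table 15.1.4 14 can arise only through hospitalisation. Table 15.1.4 11 also crosses the two counts. This largely stands: the sentences are a conflict to resolve, not proof that patients will be misassigned, and two of the three unassigned patterns are the ineligible group A.

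**Mitigation exists.** Physicians may estimate a count, so unknowns are a residual. From Sensitivity Tables 12 and 13 a reader can add C to D and subtract mean scores. This stands for point estimates, but the spread and confidence interval of the change cannot be recovered that way.

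**The footnote is only a classification convention.** The raw count is left missing, the protocol refers to available history, and it defers detail to the SAP. This fails: available history does not imply that unavailable history is zero, and the protocol groups unknown with missing.

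**The fix loses patients.** A share u(1−h·k) goes to Missing: 0.85% to 8.75% on the first set of inputs, or about 10 to 102 if applied to all 1170. No document shows that exclusion is less biased. This is a real cost, but the loss would be visible in the tables and would follow the protocol's stated rule.

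**Conclusion.** The point holds, and the SAP should be corrected. The unknown-as-zero footnote contradicts the protocol's missing-data rule and can only misclassify toward low risk. The written GOLD rule and the SAP table differ for a single hospitalised exacerbation: D against B at mMRC ≥2, and C against no group at mMRC 0–1.

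The consequences are confined to the GOLD subgroup comparisons, the baseline severity tables and the GOLD displays in Sensitivity analysis II. The overall success proportion and the sample size are unaffected. The real size cannot be computed from the documents. On the assumptions shown it is small: a true 10-point difference reads 9.98 to 9.30, or down to 8.8 on the wider inputs. These figures assume that misclassified patients have the C/D success rate, and they leave out the hospitalisation conflict, for which the documents give no frequency.

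**What to change.** 1. Delete the unknown-as-zero footnote.
2. Derive one analysis GOLD group from the raw fields, following the SAP's own table: C or D if the count is ≥2 or hospitalisations are ≥1; A or B only if the count is recorded as 0 to 1 and hospitalisations are 0; otherwise Missing, a row that Table 15.1.4 12 already has. An unknown count with a recorded hospitalisation stays in C or D.
3. Rewrite the sentences to match the table, with the hospitalisation term and a definition of A.
4. State how unknown counts are coded in the estimate flag used by Sensitivity analysis II.
5. Add an unknown-count row to Table 15.1.4 14 and Sensitivity Table 11. Hospitalisation rows there would help the reader but are largely redundant with the existing columns.
6. Compare the derived group with the eCRF group and list the differences.

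The cost is SAP wording, one derivation rule, extra rows in two tables and one cross-check. The eCRF need not be rebuilt, because Listing 3 already holds the raw fields. Patients whose group cannot be determined drop out of the GOLD subgroup tables but stay in the primary analysis.

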## 2 DISPLAY TEMPLATES

### 2.1 Display templates for in - text reports

#### 2.1.1 In-text table templates

Not applicable.

#### 2.1.1 In-text figure examples

Not applicable.

### 2.2 Display templates for in- or end-of-text reports

#### 2.2.1 End-of-text table templates

##### 2.2.1.1 15.1 Trial subject

##### 2.2.1.1.1 15.1.1 Disposition of subjects

Table 15.1.1 1: Disposition

	N (%)
Patients recruited {patient.id}	xx (100.0)
Patients with visit 1 {anamnesis.done}	xx (yy.y)
Reason for not performing Visit 1 {anamnesis.done_reason}	
Adverse event	xx (yy.y)
Serious adverse event	xx (yy.y)
Patient's wish	xx (yy.y)
Withdrawn consent	xx (yy.y)
Lost to follow-up	xx (yy.y)
Patient died	xx (yy.y)
Other	xx (yy.y)
Study participation not possible {patient.no_participation}	xx (yy.y)
Patients with visit 1, but no registration {anamnesis.done}{registration.registered_by}	xx (yy.y)
Patients not treated	xx (yy.y)
Patients included in Treated Set	xx (yy.y)
Patients with Visit 2 {visit.done}	xx (yy.y)
Reason for not performing Visit 2 {visit.done_reason}	
Adverse event	xx (yy.y)
Serious adverse event	xx (yy.y)
Patient's wish	xx (yy.y)
Withdrawn consent	xx (yy.y)
Lost to follow-up	xx (yy.y)
Patient died	xx (yy.y)
Other	xx (yy.y)
Patients with Visit 2- Continuation of medication after end of observation (Spiolto ® Respimat ® ) {visit.spolto_continued}	xx (yy.y)
Patients with Visit 2- Discontinuation of medication after end of observation (Spiolto ® Respimat ® )	xx (yy.y)
Reason for discontinuation of Spiolto ® Respimat ® {visit.spolto_reason}	
Adverse event	xx (yy.y)
Serious adverse event	xx (yy.y)
Patient's wish	xx (yy.y)
Withdrawn consent	xx (yy.y)
Lost to follow-up	xx (yy.y)
Patient died	xx (yy.y)
Other	xx (yy.y)

Patients included in FAS	xx (yy.y)
Reason for not included in FAS	
Available total CCQ score at visit 1 only	xx (yy.y)
Available total CCQ score at visit 2 only	xx (yy.y)
No available total CCQ score at all	xx (yy.y)
Not included in TS	xx (yy.y)

### 15.1.2 Important protocol violations

**Table 15.1.2 1: Patients with visit 1- Important protocol violations**

	N (%)
Total	xx (100.0)
Total with violation of informed consent { patient.ic_01 }	xx (yy.y)
Total with violation of any other inclusion criteria { patient.ic_02-patient.ic_04 }	xx (yy.y)
Total with violation of any exclusion criteria { patient.ec_01-patient.ec_05 }	xx (yy.y)
Total with violation of any inclusion or exclusion criteria { patient.ic_01-patient.ic_04; patient.ec_01-patient.ec_05 }	xx (yy.y)

**Table 15.1.2 2 Patients with visit 1- Inclusion criteria**

Inclusion criteria not fulfilled	N	%
patient.ic_01		
IC 1- Written informed consent prior to participation		
patient.ic_03		
IC 2- Female and male patients >=40 years of age		
patient.ic_02		
IC 3- Patients diagnosed with COPD and requiring a combination of two long-acting bronchodilators (LAMA+LABA) according to approved SmPC and GOLD COPD guideline recommendation 2017 (GOLD COPD groups B to D)		
patient.ic_04		
IC 4- Treatment with Spiolto® Respimat® acc. to SmPC at the discretion of the physician		
At least one inclusion criteria not fulfilled		
Number of patients	xx	100.00

**Table 15.1.2 3: Patients with visit 1- Exclusion criteria**

Exclusion criteria fulfilled	N	%
patient.ec_01		
EC 1- Patients with contraindications according to Spiolto® Respimat® SmPC		
patient.ec_02		
EC 2- Patients already on a LABA/LAMA combination (free and fixed dose) in the last 6 weeks before study entry		
patient.ec_03		
EC 3- Patients continuing LABA-ICS treatment should not be additionally treated with Spiolto® Respimat® in order to avoid a double dosing of long-acting beta-agonists		

Exclusion criteria fulfilled	N	%
patient.ec_05		
EC 4- Pregnancy and lactation		
patient.ec_04		
EC 5- Current participation in any clinical trial or any other non-interventional study of a drug or device		
At least one exclusion criteria fulfilled		
Number of patients	xx	100.00

**2.2.1.1.2 15.1.3 Definition of analysis sets**

**Table 15.1.3 1: Patients with visit 1 patients- Summary of analysis population**

Sample size	N	%
Treated Set (TS)		
Full Analysis Set (FAS)		
Patients with visit 1	xx	100.00

**2.2.1.1.3 15.1.4 Demographic data and baseline characteristics**

**Table 15.1.4 1: Treated Set- Age at registration [years]**

patient.birthyear; registration.registered_at	N (Number of non-missing values)	Mean	SD	Min	Median	Max	Nmiss (Number of missing values)
Age at registration							

**Table 15.1.4 2: Treated Set- Age at registration, categorical**

patient.birthyear; registration.registered_at	N	%
Age, categorical		
<65 years		
≥65 years		
Missing		
Number of patients		

**Table 15.1.4 3: Treated Set- Gender**

patient.gender	N	%
Gender		
Male		
Female		
Number of patients		

**Table 15.1.4 4: Treated Set- Height [cm]**

patient.bodysize	N	Mean	SD	Min	Median	Max	Nmiss
Height							

**Table 15.1.4 5: Treated Set- Weight [kg]**

patient.bodyweight	N	Mean	SD	Min	Median	Max	Nmiss
Weight							

Visit 1- Baseline

**Table 15.1.4 6: Treated Set- Duration between initial diagnosis of COPD and baseline visit [years]**

anamnesis.date; anamnesis.copd_year	N	Mean	SD	Min	Median	Max	Nmiss
Duration between initial diagnosis and baseline visit							

**Table 15.1.4 7: Treated Set- COPD degree of severity (spirometric)**

anamnesis.copd_severity	N	%
COPD degree of severity (spirometric)		
1		
2		
3		
4		
No preliminary examination result		
Missing		
Number of patients in Treated Set		

**Table 15.1.4 8: Treated Set- COPD degree of severity (spirometric) [grouped]**

anamnesis.copd_severity	N	%
COPD degree of severity (spirometric) [grouped]		
1/2		
3/4		
No preliminary examination result		
Missing		
Number of patients in Treated Set		

**Table 15.1.4 9: mMRC Questionnaire**

mmrc.activity	N	%
mMRC Questionnaire		
Grade 0		
Grade 1		
Grade 2		
Grade 3		
Grade 4		

mmrc.activity	N	%
mMRC Questionnaire		
Missing		
Number of patients in Treated Set		

**Table 15.1.4 10: Treated Set- Exacerbations and hospitalizations due to exacerbations in the last 12 months**

Exacerbations and hospitalizations due to exacerbations in the last 12 months	Number of patients	Number of exacerbations	Mean	SD	Min	Median	Max	Nmiss	Patients with events	
									N	%
anamnesis.exacerbation										
Number of exacerbations										
anamnesis.exacerbation_hospital										
Number of hospitalizations due to exacerbations										

**Table 15.1.4 11: Treated Set- Exacerbations and hospitalizations due to exacerbations in the last 12 months, categorical**

anamnesis.exacerbation; anamnesis.exacerbation_hospital		Hospitalizations due to exacerbations in the last 12 months								Number of patients in Treated Set			
Exacerbations- Overview		0		1		2		...		N		%	
		N	%	N	%	N	%	N	%				
Exacerbations in the last 12 months	0												
	1												
	2												
	...												
Number of patients in Treated Set													100.0

**Table 15.1.4 12: Treated Set- COPD degree of severity (GOLD group)**

COPD degree of severity (GOLD group)	N	%
A		
B		
C		
D		
Missing		
Number of patients in Treated Set		

